Dietary Intake: Dietary and supplement intake data will be at baseline for a week in tandem with cognitive bursts and in three follow-up bursts of one week at each follow-up clinic visit collected using the ASA24 (68) We chose this method as it has low participant burden and can be completed in real-time and has been used by participants with diverse backgrounds (70). Improvements in technology now allow for digital images that assist with estimation of serving size (71). The ASA24 has been validated against interviewer-administered 24-hour dietary recalls and is available in both English and Spanish and includes audio to guide the user (72). Participants will be prompted to go online via smartphones to complete the assessment. Participants will undergo training to use the ASA24 at the run-in visit. The food database for ASA24 is from the Food & Nutrition Data Base for Diet Studies (FNDDS 11-12). If participants cannot find their foods in this system, they can use the “food not found functions” to list the foods and they can be added later.

Dietary & Other Biomarkers: Blood specimens will be collected close to the baseline visit and approximately 9 months later and frozen at minus 70 degrees C and sent to Advanced Research & Diagnostic Lab (ARDL) at University of Minnesota for the following analyses: Lipid panel [cholesterol (total), HDL (direct), triglycerides, LDL (calc)]; plasma tocopherols/carotenoids; serum folate; serum B12; plasma fatty acids; IL-6 and C-reactive protein, and APOE4. To assess

hydration, serum sodium and blood urea nitrogen (BUN) were added. To ascertain type 2 diabetes we added Hemoglobin A1C. A 5% blinded duplicate sample will be sent to the lab for quality control.

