Beginning with the Covid-19 pandemic on March 13, 2020 all group intervention and comparison sessions were conducted on Zoom. Before the start of the Covid-19 pandemic, in-clinic measures were obtained during site visits that occurred prior to a 2-day baseline “Run-in” period (Run-in Visit), a 7-day Baseline measurement burst (Baseline Visit), 9-, 18-, and 27-month measurement bursts (Follow-up Visits). Beginning with the pandemic all cognitive assessments were conducted online via Zoom except for the NIH Toolbox which was discontinued. We resumed biospecimen collection and anthropometry in-person starting July 16, 2020, after a four month hiatus due to the pandemic.

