6.2.3 Follow-up visits

Clinic Visit #1 (Scheduled for eligible participants after Screening Visit #2, 2 hr)

At this visit, participants will:

- undergo cognitive testing at the clinic
- respond to questionnaires about medical history, moods & daily experiences
- receive randomization assignment to Usual Diet or Multicultural Healthy Diet
- schedule a 30 minute visit for eye test and body measurements: blood pressure, blood draw, spot urine collection, height, weight, waist/hip circumference, body composition.

At home after Visit #1 (1 hour per day for 7 days)

Participants are asked to do the following over the next seven days:

- enter food intake using the smartphone
- complete a brief survey when waking up in the morning and before going to bed
- play brief brain games four times during the day
- at the end of the 7 days, return the smartphone to the clinic after completing the exercises

Randomization

Randomization occurs after Clinic Visit #1 (Baseline) when body measurements are complete. When adequate numbers of participants (about 8-10) are randomized to start a comparison or intervention group, participants will be invited to the sessions. In the meantime they will receive informational materials about the study in preparation for the sessions.

Clinic Visit #2 (Scheduled 9 months after Visit #1, 2 hr)

This visit is identical to Visit #1.

At home after Visit #2 (1 hour per day for 7 days)

These activities are identical to at-home activities after Visit #1.

Clinic Visit #3 (Scheduled 9 months after Visit #2, 2 hr)

This visit is identical to Visit #1, except that there will be no blood tests or urine collection scheduled after the visit.

At home after Visit #3 (1 hour per day for 7 days)

These activities are identical to at-home activities after Visit #1.

Clinic Visit #4 (Scheduled 9 months after Visit #3, 2 hr)

This visit is identical to Visit #1, except that there will be no blood tests or urine collection scheduled after the visit.

At home after Visit #4 (1 hour per day for 7 days)

These activities are identical to at-home activities after Visit #1.

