where b_{ij} is the person level effect (random intercept term) for participant i and Burst j , and e_{ijk} is the residual error term assumed to be mean 0, independent across time and individuals and approximately normally distributed. In this model, response Y_{ijk}^d is modeled as a function of the overall baseline level and the term β_4 summarizes the potential treatment effect on the change over time. Models will be further adjusted for age, gender, APOE4 allele, race, and ethnicity in supportive analyses. The difference in time and underlying cognitive function within a burst is assumed negligible, thus the time and season variables in these models will be determined by the first day of the Burst.

The Color Shapes task has only 7 possible values, so a similar generalized estimating equation (GEE) approach will be taken using the Poisson mean model and robust sandwich variance for the number of incorrect responses (0-6).

Our secondary outcomes also include between arm comparisons of MHD-related dietary intake based on self-report and biomarker measures of intake at 9 months post baseline. Outcome models of between-arm differences in dietary intakes indicative of the MHD as measured by nutritional biomarkers, and self-report at Burst 2 will be conducted in a similar manner to the models specified above for the primary cognitive outcomes: namely, ANCOVA models that adjust for the baseline level, Arm and stratification factors will be fit. Tocopherols and carotenoids plasma biomarkers will be additionally adjusted for cholesterol variables per Gross et al (2003). Longitudinal models considering ASA24 data across the 4 bursts will be fit using similar mixed effects models, simplified to analyze only the Burst level average for the ASA24 dietary intakes (no repeated measures within a burst). Analyses will generally be complete case

analyses for the dietary variables. Energy adjustment will be considered where appropriate. Sensitivity analyses with additional adjustment variables associated with missing, as well as exploratory analyses that examine potentially differences in intervention effect by gender, race, ethnicity and age, will also be considered.

The plasma biomarkers include: total folate, alpha and gamma tocopherol, carotenoids (alpha carotene, beta carotene, zeaxanthin+lutein, beta cryptoxanthin, and vitamin B12), lycopene, and fatty acid profile. Serum sodium is an additional secondary outcome, indicative of hydration.

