For randomized trials, under the MAR assumption and when only the outcome variable is missing, complete case analyses that additionally adjust for all the variables related to the missingness imputation will be consistent and can be the most efficient analysis (Little et al, 2022). Thus for the secondary endpoints, the adjustment approach will be considered. For the repeated measures models of the cognitive outcomes, the proposed adjusted analysis models are as described above (Model 1 and Model 2). For the dietary biomarker and self-reported ASA-24 outcomes, adjustment for baseline demographics (age at Burst 1, gender, race, ethnicity, years of education, MOCA score, indicator for in-person vs telephone MOCA, and interaction between the two MOCA variables, and BMI. Energy adjustment will be considered as appropriate for the dietary component. In particular, parsimonious outcome models that include adjustment of variables when found to be associated with missingness will be considered. Analysis of tocopherols and carotenoids plasma biomarkers will be additionally adjusted for cholesterol variables per Gross et al (2003).

References

Van Buuren, S. (2018). *Flexible imputation of missing data.* CRC press.

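### The complete-case rule for the dietary biomarkers is justified for missing outcomes only, but baseline blood and BMI may also be missing after the 2020 stop, and the SAP has no rule for that

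*SAP*

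**What the plan says.** In the SAP section on the missing-data approach for secondary outcomes, the premise is that under MAR, "when only the outcome variable is missing, complete case analyses that additionally adjust for all the variables related to the missingness imputation will be consistent". The SAP adds that such an analysis can be the most efficient one. It then concludes: "Thus for the secondary endpoints, the adjustment approach will be considered". The Analysis of Secondary Outcomes section says of the dietary variables that "Analyses will generally be complete case", and of the biomarker models that "ANCOVA models that adjust for the baseline level, Arm and stratification factors will be fit". Both sections add cholesterol variables for tocopherols and carotenoids. The missing-data section also lists BMI among the adjustment variables for the biomarker and self-reported intake outcomes.

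On the blood itself, Protocol section 3 says "Blood specimens will be collected close to the baseline visit and approximately 9 months later", so there are two draws and no others. Under Adaptations to the Pandemic it records: "We resumed biospecimen collection and anthropometry in-person starting July 16, 2020, after a four month hiatus due to the pandemic". Group sessions and most cognitive testing moved to Zoom over that period.

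On the order of events, Protocol 6.2.3 says "Randomization occurs after Clinic Visit #1 (Baseline) when body measurements are complete", and its list of body measurements includes the blood draw. The SAP's Randomization section agrees. Yet the Visit #1 list in 6.2.3 has participants receive their assignment at that visit, where the blood-draw appointment is only scheduled.

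**The concern.** The stated premise covers a missing outcome. It does not cover a missing covariate, and this model's main covariate is a second blood sample exposed to the same interruption as the first. Baseline BMI, and baseline cholesterol if that is what the cholesterol adjustment means, depend on the same visit. A participant with a valid 9-month sample and no baseline value would leave the comparison, although the outcome was observed and the arm is known. The claim that complete case can be the most efficient analysis does not extend to that situation.

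The biomarkers are the objective evidence for specific aim A1, and Protocol 9.2 introduces the dietary comparisons as key secondary outcomes. The SAP's version date of 9/7/2023 is about three years after the interruption. It imputes short Burst 1 as well as Burst 2 scores for the primary outcome, but gives no rule for a missing baseline biomarker or BMI.

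**Working it through.** **Inputs.** From Protocol 9.2: effect size 0.35 SD, 125 per arm (250 in all), within-person correlation ρ of at least 0.5, 80% power. Two-sided α = 0.05 is assumed, because the documents state none.

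**The plan's own figure.** At ρ = 0.5 the SD of a change is SD × √(2(1 − 0.5)) = SD. The detectable differences are then 0.35 × 17 = 5.95 nmol/L, 0.35 × 0.28 = 0.098 mg/dL and 0.35 × 330 = 115.5 pg/mL, which match the Protocol. Power is Φ(0.35 × √(125/2) − 1.96) = Φ(0.807) = 79.0%, so the stated 80% reproduces.

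**Share without a baseline (assumption).** The documents give neither a count nor an accrual period. If accrual ran evenly for 36 to 48 months and continued through the four-month stop, the share f is 4/48 = 8.3% to 4/36 = 11.1%. If randomization paused or the gating rule was enforced, f could be near zero.

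**Cost of dropping them.** In units of the outcome variance, the ANCOVA residual variance is 1 − ρ² = 0.75 with a baseline and 1 without. Information on the arm contrast is proportional to:

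- complete case: 250(1 − f)/0.75
- all 9-month samples kept: 250(1 − f)/0.75 + 250f

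| f | Dropped | Complete case | All kept | SE ratio |
|---|---|---|---|---|
| 8.3% | 20.8 | 305.6 | 326.4 | √(326.4/305.6) = 1.034 |
| 11.1% | 27.8 | 296.3 | 324.1 | √(324.1/296.3) = 1.046 |

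The complete-case SE is therefore about 3.4% to 4.6% larger.

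**Power over a wider range of f** (N = 250, ρ = 0.5, effect 0.35 SD):

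| f | ANCOVA, complete case | ANCOVA, all kept |
|---|---|---|
| 0 | 89.2% | 89.2% |
| 5% | 87.6% | 88.8% |
| 10% | 85.8% | 88.4% |
| 20% | 81.5% | 87.6% |

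Keeping these participants recovers a fraction 1 − ρ² of the lost information: 75% at ρ = 0.5 and 51% at ρ = 0.7.

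**Bias check.** This used 4,000 simulated trials with N = 260 (the number reached at Visit 2), true effect 0.35, ρ = 0.5 and 15% of baselines missing independently of arm and outcome.

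| Analysis | Mean estimate | Empirical SD | Power |
|---|---|---|---|
| Complete case | 0.352 | 0.1158 | 85.6% |
| Missing indicator | 0.353 | 0.1094 | 89.1% |
| Full data | 0.353 | 0.1071 | 90.3% |

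Neither method is biased in this setting. The SD ratio is 0.1158/0.1094 = 1.06. The formula gives √(1 + 0.15 × 0.75/0.85) = 1.06 at f = 15%.

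**The case against.** The strongest reply is the gating rule. If nobody was randomized until body measurements, including blood, were complete, a participant caught by the stop simply waited, and no baseline is missing. The SAP repeats that order. The Protocol says that sessions and testing went online; it does not say that randomization continued, and no section reports a missing or late baseline sample. This stands as a limit on size: the documents support saying that baselines may be missing, not that they are. It does not close the gap. Section 6.2.3 also has the assignment received when the draw is only scheduled, section 4.3 places randomization after screening visit #2, and section 3 has devices returned after the burst when participants come back for blood.

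A second reply is that the plan is not silent. Complete case applies only generally, extra adjustment for variables associated with missingness will be considered, and sensitivity analyses may be run above 10% missingness. BMI is not in the main ANCOVA and might not survive the parsimonious selection. That is fair, but these provisions are optional, and adding covariates does not bring back dropped participants.

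A third reply is that complete-case ANCOVA stays consistent when a calendar stop, unrelated to outcome given the covariates, removes baselines. This is correct, and power on the ANCOVA basis stays above 80% even at 20% missing.

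**Conclusion.** The gap is real and modest. The stated justification does not reach the model's own baseline covariates, a documented event put them at risk, and following the plan would discard observed 9-month samples. The loss is precision: an SE about 3.4% to 4.6% larger at f = 8% to 11% of 250 and ρ = 0.5, and nothing if f is zero.

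A reader might infer three stronger things that the documents do not support:

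- **That the complete-case condition has failed and participants have been lost.** It is not assured, which is a weaker statement.
- **That the arm effect is biased by the missing baselines.** A stop that follows the calendar gives no reason to expect this.
- **That late baseline draws shrink the arm effect.** The shrinkage would be f times the baseline slope, 0.083 × 0.5 = 4.2% to 0.111 × 0.5 = 5.6%. That is an upper bound, since every affected participant would need a late draw already carrying the full diet effect. Section 6.2.3 also holds group sessions until about 8 to 10 participants have been randomized, which makes a draw after the first session less likely.

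**What to change.** In the SAP sections Analysis of Secondary Outcomes and Missing data approach for the secondary outcomes:

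- Include every randomized participant with a 9-month sample in the biomarker ANCOVA.
- Fill a missing baseline biomarker or baseline BMI with the overall mean across both arms and add a missing indicator, or use multiple imputation as for the primary outcome. Treat baseline cholesterol the same way if that is the intended covariate.
- Keep complete case as the sensitivity analysis.
- Report baseline and 9-month sample availability by arm. The indicator method relies on missingness being unrelated to arm, and this table is the check.
- Address baseline samples drawn after the first session in a sensitivity analysis only. That timing is post-randomization and may differ by arm as groups fill, so recoding such samples as missing in the main analysis would not be protected by randomization.

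The cost is a few sentences in the SAP, a comparison of draw dates with first-session dates, and slightly more analysis work, with no new data. The drawback is a single-fill covariate model that some statisticians would replace with multiple imputation; either is acceptable if chosen in advance.
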